5. STUDY DESIGN

5.1. Summary Protocol

Patients with any type of cancer scheduled to receive anti-cancer therapy with or without concomitant radiotherapy and enrolled in the SURVIVE Registry will be evaluated based on baseline MyoStrain® segmental dysfunction risk profile. After consenting to the PROACT study, patients will undergo a baseline MRI to determine their risk stratification for the study. This baseline MyoStrain® MRI must demonstrate 2 or more segments measuring >-10% or 9 or more segments >-17% for entrance into the study.

[figure not shown]
Eligible patients will then be randomized 1:1 into the MyoStrain® guided treatment arm versus the Myostrain® blinded observational arm, as shown in Figure 2. The treatment arm will guide patient management by augmenting standard of care with serial MyoStrain® monitoring of the impact of cancer therapy on myocardial function by providing physicians with MyoStrain® values, in addition to LVEF, LVEDV, and LVESV. In the

observational arm, physicians will only be provided with LVEF, LVEDV, and LVESV, which are clinical measurements. The standard of care assessments by cardiac MRI, will not include MyoStrain® assessments.

In order to obtain the MyoStrain® values, MRI images obtained will be uploaded de-identified to Myocardial Solutions, Inc. After the baseline scan, Myocardial Solutions, Inc. will inform research staff whether the patient met criteria for continued follow up in the study. At that time, the patient will be randomized to one of the two arms, as previously described, and Myocardial Solutions, Inc. will be made aware of the randomization result. If randomized to the blinded observational arm, no results from any cardiac MRI obtained for the study will be provided to physicians from Myocardial Solutions, Inc. If randomized to the MyoStrain® guided treatment arm, MyoStrain® results and LVEF, LVEDV, and LVESV will be provided for all cardiac MRI's obtained in the study to the physicians. Sites will also send Myocardial Solutions, Inc. de-identified information about the patients' medical history (i.e. comorbidities, past/current medications, etc.).

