5.7. Sample size

40 evaluable patients will be randomized 1:1 to the MyoStrain® imaging guided arm versus the standard of care arm.

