The longitudinal data will be compared for each individual with his/her baseline, to learn and guide each individual's care and to infer the level of cardiotoxicity. The same group's data will be analyzed with the intention in identifying what trends exist among those in the group of MyoStrain SENC software guided treatment. The full cardiac measures for the other group: the observational arm will be available to us at the end of the trial. At that time, we will analyze also the longitudinal cardiac 3D features for this group at the individual levels compared to baseline. In addition, we will analyze the longitudinal data to identify trends for each group, as well as we will compare trends of two groups toward cardiac response to chemotherapy and / or radiology. We will test the cardiotoxicity development i.e. myocardial dysfunction by comparing the efficacy of detecting cardiac dysfunction using standard assessments LVEF, LVESV and LVEDV in time against analyzing all cardiac features collected via MyoStrain (more than 60 of them, Figure 5). Multivariate regression and logistic regression will be used with "stepwise" option to identify significant predictors at standard and guided care features for predicting cardiotoxicity. Furthermore, we will use decision trees for identifying the

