Based on pilot data and utilizing only the moderate to high risk group (>2 segments of Myostrain determined segments >17%), the outcome expected would be 12.8 +/- 4.7 dysfunctional segments for the intervention group and 16.8 +/- 7.8 dysfunctional segments for the control group (and using average of 4.7 and 7.8 for the standard deviation for the overall outcome) at 6 months. This same parameter will be followed at the other time points, including 1 year, 2 years, and 3 years, but the primary endpoint will be at 6 months. With these calculations, 102 patients are required to have a 90% chance of detecting, as significant at the 5% level, a decrease in the primary outcome measure from 16.8 in the control group to 12.8 in the experimental group (number of dysfunctional segments (>17%)).

The sensitivity, specificity, and diagnostic accuracy of each reader to detect changes in myocardial function will be determined for quantitative SENC-CMR. Cutoff-values used to calculate sensitivity and specificity of the quantitative SENC parameters were determined using data previously published. The cutoff for the % of MyoStrain segments <= -17% (based on 37 left ventricular segments) in detecting subclinical cardiotoxicity in the PREFECT50 planned interim analysis was 68% and the cutoff for detecting clinical cardiac dysfunction was 49%; a cutoff of 80% differentiates normal cardiac function from patients experiencing functional decline. McNemar's test with continuity correction will be used to compare the diagnostic performance of each of the SENC-CMR cutoff parameters. Additionally, Receiver Operating Characteristic curves as well as Precision Recall curves will be generated to calculate and compare the area under the curves to determine the diagnostic performance of changes in strain parameters and standard assessments. Inter- and intra-observer variability will also be determined for each of the above parameters using intraclass correlation.

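### No model is named for the 6-month segment count, and nothing commits the plan to use the baseline count that every randomised patient has

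*Combined protocol and SAP*

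**What the plan says.** Section 11 (Statistical Considerations) sizes the trial on the number of dysfunctional segments, read here as segments with strain above -17%, the threshold used elsewhere in the protocol. It expects "12.8 +/- 4.7 dysfunctional segments for the intervention group and 16.8 +/- 7.8 dysfunctional segments for the control group", takes the SD by "using average of 4.7 and 7.8 for the standard deviation for the overall outcome", and concludes that "102 patients are required to have a 90% chance of detecting, as significant at the 5% level", the target being "a decrease in the primary outcome measure from 16.8 in the control group to 12.8 in the experimental group". The count is to be followed at later visits, "but the primary endpoint will be at 6 months". Section 5.7 now states that "40 evaluable patients will be randomized 1:1"; the calculation in Section 11 still carries 102.

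Section 5.1 makes the baseline scan the gateway to randomisation: it "must demonstrate 2 or more segments measuring >-10% or 9 or more segments >-17% for entrance into the study". A baseline count is therefore on file for everyone randomised.

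On analysis, Section 11 says that "The longitudinal data will be compared for each individual with his/her baseline" in order to guide that patient's care and infer toxicity. It also plans to compare longitudinal trends between the two groups, and it lists the SAS procedures GLM, LOGISTIC and MIXED, the last for repeated measures. It adopts intention to treat. It does not name a response, covariates or a contrast for the 6-month count. The only covariates it mentions outside predictor selection are those that may help impute missing data.

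**The concern.** The baseline count is the same measurement as the outcome, taken before randomisation, and is an obvious candidate covariate. If it predicts the 6-month count, adjusting for it removes part of the residual variance and corrects for chance imbalance between arms. With 20 patients per arm both matter. For illustration, the pilot's baseline SD for this count was 4.7 (Section 2.3, all 15 patients). If that SD applied here, the between-arm baseline difference would have a standard error of 4.7 × √(2/20) = 1.5 segments, against a planned effect of 4.

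The plan neither requires nor excludes this adjustment. As written, a raw t-test and a baseline-adjusted model are equally compatible with the text, they can differ materially in power, and the choice could be made after the data are seen.

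**Working it through.** **Inputs.** Difference 16.8 - 12.8 = 4.0. SD (4.7 + 7.8)/2 = 6.25. Significance level 5%, power 90%, total 102 (all Section 11). Allocation 1:1 and 40 evaluable patients, so 20 per arm (Section 5.7). Sidedness is not stated.

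**Step 1: reproduce 102.** For two unadjusted means under the normal approximation, n per arm = 2 × (1.960 + 1.282)² × 6.25² / 4² = 51.3, or 102.6 in total. Rounded up by arm this is 104, within two patients of the plan. Power at 51 per arm is 89.8%. A one-sided test gives 84. A root-mean-square SD, √((4.7² + 7.8²)/2) = 6.44, gives 110. The plan's figure is thus a two-sided comparison of raw means with SD 6.25 and no baseline term.

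**Step 2: unadjusted power at the current size.** The standard error is 6.25 × √(2/20) = 1.98, and 4/1.98 = 2.02. Power is 50.5% by noncentral t, or 52.5% by the normal approximation.

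**Step 3: power with baseline as covariate.** Residual SD = 6.25 × √(1 - r²), where r is the within-arm correlation of baseline and 6-month counts. One further degree of freedom is spent, leaving 37. The documents give no r, so a range is assumed. The equivalent gain in patients is 1/(1 - r²) - 1.

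| r (assumed) | Residual SD | Power, 20 per arm | Equivalent gain in patients | Total N for 90% power (normal approx.) |
|---|---|---|---|---|
| unadjusted | 6.25 | 50.5% | – | 104 |
| 0.3 | 5.96 | 54% | 10% | 94 |
| 0.5 | 5.41 | 62% | 33% | 78 |
| 0.6 | 5.00 | 69% | 56% | 66 |
| 0.7 | 4.46 | 79% | 96% | 54 |

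**Step 4: sensitivity to the SD.** With 6.44 in place of 6.25, unadjusted power is 48%, and adjusted power is 52%, 60%, 67% and 76% at the same correlations. The conclusion is unchanged.

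**Step 5: can adjustment restore 90% at 40 patients?** The largest residual SD that allows it is 4 / (√(2/20) × 3.242) = 3.90 (normal approximation). This needs r = √(1 - (3.90/6.25)²) = 0.78. By noncentral t, r = 0.8 gives 90.7%.

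**The case against.** The strongest reply is that the 16.8 versus 12.8 sentence sets a sample size and names no test. Sizing on raw means and then analysing with adjustment is common and conservative. Section 11 also plans group trends, GLM and a repeated-measures MIXED model, any of which could carry the baseline. This part stands. A reader might infer that the analysis itself is planned on raw means and that power is definitely lost. The documents show raw means only for the sizing and leave the analysis open, so the loss is a risk and not an established fact.

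Naming MIXED does not close the gap, however. If the model has a free mean for each arm at each visit, baseline included, its 6-month contrast with complete data is simply the raw mean difference. Whether baseline is used depends on a specification that the plan does not give.

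A reader might also take the sentence about comparing each patient with baseline as a between-arm test of change scores. It describes monitoring of individuals, and no change-score test between arms is proposed anywhere. Nor do the documents support a claim that such a test would do worse than raw means: that depends on the unknown correlation and on the baseline SD among randomised patients, which is not given.

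Finally, the correlation may be low. Entry selects on the baseline segments, which can restrict their range, and cancer therapy comes before the 6-month scan. This stands too: at r = 0.3 the gain is only about 4 percentage points. But adjustment costs almost nothing even at low r; at an assumed 0.2, power is 52.1% against 50.5%.

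**Conclusion.** The point holds as a gap in specification with a nearly free remedy. The only between-arm comparison defined for the 6-month count is the sizing comparison of unadjusted means. No text makes the baseline count a covariate, and the count exists for every randomised patient.

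On the plan's own SD and difference at 20 per arm, adjustment would move power from about 50% to somewhere between 54% and 79% for correlations of 0.3 to 0.7. The direction is secure unless the correlation is close to zero; the size is unknown. The figures assume a two-sided 5% test, a common SD of 6.25, an unchanged difference of 4, and 20 patients per arm with both scans.

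Two limits apply. Adjustment does not cure the reduction from 102 to 40 patients: a correlation of nearly 0.8 would be needed for 90% power, so the sample size needs its own justification. And Section 1.5 names diagnostic sensitivity and accuracy as the primary efficacy endpoint, while Section 11 places the primary endpoint on the 6-month count. That conflict must be reconciled separately, and until it is, the standing of this contrast is uncertain.

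**What to change.** Add a statement to Section 11: the number of segments with strain above -17% at 6 months is compared between arms as randomised, adjusted for the baseline count. Name one method: ANCOVA, or the already planned MIXED model with baseline count as covariate, arm-by-visit terms and the 6-month arm difference as the named contrast. Give the assumed baseline-to-6-month correlation, with its source, wherever adjusted power is quoted.

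The cost is a sentence or two of text and one degree of freedom. No new data, visits or software are needed.

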12. DATA MANAGEMENT

The coordinating center and primary investigator are responsible for data management. The investigator/clinical coordinator at each participating site will be responsible for completion and timely input of the study data into the WUSTL REDCap database. Data entered will be reviewed to identify inconsistent or missing data and Adverse Events. The Investigator at each participating site is to maintain all source documents as required by the protocol, including SENC MyoStrain® results, supporting medical records, and Informed Consents.

Confidentiality of data shall be observed by all parties involved during the research. The privacy of each subject and confidentiality of his/her information shall be preserved in reports and when publishing any data.

13. DEVICE ACCOUNTABILITY

Records shall be kept to document when the SENC software and pulse sequence patch is received, returned, uninstalled or disposed at the participating sites.

14. STATEMENTS OF COMPLIANCE

This study will be conducted according to good clinical practice guidelines, the Declaration of Helsinki, and the ANSI ISO 14155: clinical investigation for human subjects. Written informed consent for the study will be received from all participants.

15. INVESTIGATOR RESPONSIBILITIES AND OBLIGATIONS

15.1. Investigator Responsibilities

The Investigator is responsible for obtaining the initial and continuing review and approval from the authorized IRB/Ethics Committee for the participating site at which the proposed clinical investigation is to be conducted. The Investigator is responsible for ensuring that informed consent is obtained from each study subject prior to the initiation of any study procedures.

15.2. Investigator Records

The Investigator will maintain complete, accurate and current study records, including the following materials:

- 1) Study Subject Records, including Informed Consent forms, supporting source documents, and CMR image files including MyoStrain® reports;
- 2) All relevant observations, including records concerning adverse device effects (whether anticipated or unanticipated);
- 3) Current study protocol and protocol deviation log, with dates and details of any reason for deviations from the protocol that could affect the scientific quality of the study or the rights, safety, or welfare of the subjects;
- 4) The approved blank Informed Consent form and Case Report Forms (CRFs); and
- 5) Documentation that the Investigational Plan has been approved by all of the necessary approving authorities.

15.3. Investigator Reports

The Investigator will be responsible for the following reports:

- **Unanticipated Adverse Device Effect:** The Investigator shall report all Unanticipated Adverse Device Effects to the Sponsor and to the reviewing IRB as soon as possible, but no later than 10 working days after the Investigator first learns of the effect. All Unanticipated Adverse Device Effects should be documented by time of onset, a complete description of the event, severity, duration, actions taken and event outcome.
- **Withdrawal of IRB/EC Approval:** The Investigator shall report to the Sponsor within 5 working days if, for any reason, the IRB/Ethics Committee withdraws approval to conduct the investigation. The report will include a complete description of the reason(s) for which approval was withdrawn.
- **Deviations from the Investigational Plan:** The Investigator shall notify the Sponsor and the reviewing IRB of any changes in, or deviations from, the Investigational Plan to protect the life or physical well-being of the Subject in an emergency. Such notice shall be given as soon as possible, but no later than 5 working days after the emergency occurs.
- **Final Report:** The Investigator will submit a final report to the Sponsor and to the IRB/EC within 3 months of termination of the study or termination of that Investigator's participation in the study.

15.4. Financial Disclosure by Clinical Investigators

Pursuant to 21 CFR part 54 and prior to the initiation of the study, each investigator must disclose certain financial arrangements that may exist between that investigator and Myocardial Solutions. This information will be collected from each investigator, maintained in confidential files at Myocardial Solutions and will be available for review by regulatory agencies upon request.

17. APPENDICES

17.1. Patient Satisfaction Questionnaire

Patient Satisfaction Questionnaire

Completion Date: _____ Participant ID: _____

Visit: Baseline 1 month 3 month 6 month
 12 month 24 month 36 month

Please answer these questions to the best of your ability. There are no right or wrong answers. All information is kept strictly confidential.

	Strongly Agree	Agree	Disagree	Strongly Disagree	Not Applicable
It was easy to schedule a convenient appointment.					
The staff was courteous and helpful.					
The time in the waiting room was reasonable.					
I feel burdened participating in this study.					
I am glad I am participating in this study.					

Questionnaire completed by:

- Patient
- Study personnel with patient
